## **INTRODUCTION**

In one study, the muscle strength of the quadriceps and hamstring, which were tested with the isokinetic muscle strength test, were found to be lower in patients with multiple sclerosis (MS) than the controls (1). In another study, bilateral muscle strength of the quadriceps and hamstring were shown to be related with walking speed, balance, and functional capacity (2). Therefore, the authors concluded that muscle strengthening exercises for the quadriceps and hamstring should be included in the rehabilitation program of MS patients.

It is known that slowing afferent proprioceptive conduction and impaired central integration of the proprioception are the main causes of balance deficit in MS patients. Proprioception impairment, often seen in patients with MS, negatively affects the joint position sense (JPS), balance, and posture. Joint repositioning, muscle strengthening,

plyometric, balance, coordination and vibration exercises are recommended to improve JPS, proprioception, and balance in this patient group (3).

It has been reported that exercise training improves and/or maintains functional capacity, strength, endurance, fatigue, quality of life (QoL), depression, cognition, and chronic disease risk factors among MS patients. The current evidence suggests that exercise training is generally safe for MS patients and not associated with an increased relapse risk. Resistance and endurance training modalities are the major types of exercises in MS patients (4).

There are not enough studies on isokinetic muscle strengthening exercises in MS patients with muscle weakness. Robineau et al. (5) and Aubry et al. (6) reported that isokinetic knee flexion-extension exercises improved quadriceps and hamstring muscle strength and control of the knee in this patient group. Manca et al. (7) investigated the efficiency of isokinetic ankle dorsiflexor training, and the muscle strength of ankle dorsiflexors improved significantly in MS patients.

Kinesiophobia is defined as “an excessive, irrational and debilitating fear of physical movement and activity resulting from a feeling of vulnerability to painful injury or reinjury” and is related with the disability level (8). MS patients show fear avoidance beliefs and behaviors which are related with pain. Although catastrophizing and fear avoidance beliefs and behaviors have been reported in MS patients, they have not been investigated in detail (9).

To the best of our knowledge, no study has explored the effects of isokinetic training on knee JPS, pain, kinesiophobia, and QoL in MS patients. Therefore, in the current study, we aimed to observe the knee JPS and kinesiophobia level, their relationships with QoL, and the effects of isokinetic exercises on these variables.

## **METHODS**

Following the Helsinki Declaration, the study was approved by the Ethics Committee of Ankara Training and Research Hospital, Health Sciences University (29.07.15, 603/5070). This prospective randomized controlled trial aimed to recruit 60 patients with MS from the physical medicine and rehabilitation clinic of Ankara Training and Research Hospital, Health Sciences University, Ankara, Turkey (June 2016 to June 2017).

### **Participants**

Individuals were included if they had definite relapsing remitting MS and secondary progressive MS diagnosis, mild and moderate MS determined by Kurtzke Expanded Disability Status Scale (EDSS) scores below 6.5, and a disease duration of more than one year. The exclusion criteria were; having an acute exacerbation within the last three months, intravenous pulse steroid therapy in the last four weeks, grade 3-4 spasticity according to the Modified Ashworth Scale, severe vision impairment, severe fatigue and depression, past knee surgery, other neurologic diseases, systemic diseases, pregnancy, and having received an exercise program within the last four weeks. Fifty patients who met the inclusion criteria were enrolled in the study (Figure 1).

### **Procedure**

Fifty patients were randomized to two groups: isokinetic exercise (Group 1) (n=25) and home exercise (Group 2) (n=25). Randomization was completed using sequentially numbered, opaque envelopes by the investigator. All patients gave informed consent before the assessment. The outcome measures were assed initially and at eighth week after the treatment. Group 1 performed isokinetic concentric quadriceps and hamstring strengthening exercises under supervision and Group 2 performed lower extremity muscle strengthening and balance exercises at home.

### **Outcome measures**

The patients completed the questionnaire about age at diagnosis, disease duration, type of disease, and medical history.

#### **Muscle strength and JPS testing**

Muscle strength and knee JPS were tested by an isokinetic dynamometer (Biodex System 3 Pro Multijoint). Before muscle strength and knee JPS testing, the patients were informed about the procedure. First knee JPS was tested, and then muscle strength was measured. The machine was calibrated before the procedure. Before muscle strength testing, the patients performed quadriceps and hamstring stretching exercises and on-site counting for five minutes for warming-up. The seat angle was set to 85° and the patient was asked to sit down. Appropriate parts for knee testing were placed in the dynamometer. The lateral femoral condyle, which is the rotation axis of the knee, was aligned to the rotation axis of the dynamometer. The patients were stabilized by thoracic, pelvic and thigh belts. The patient's leg was bound to the leverage equipment from the upper part of the medial malleolus. During

the test, the patients were asked to place their arms sideways. After determining the range of motion and gravity correction for the mass of the limb, the patients performed three submaximal warm-up contractions at 60°/s angular velocity. After warming up, the patients rested for 10 seconds, and then performed five maximal concentric knee flexion-extension at 60°/s and 10 maximal concentric knee flexion-extension at 180°/s angular velocities, separated by 20 seconds of seated static recovery. Both the more and less affected legs were tested in order, two minutes after the seated static recovery period. During the test, the quadriceps and hamstring peak torque (PT), the peak torque (PT)/body mass index (BMI), and the hamstrings/quadriceps (H/Q) ratio were evaluated at 60°/s and 180°/s angular velocities in Newton/meter (N/m) (10).

After the preparation, positioning and stabilization, knee JPS was tested according to the active-active angular reproduction method. The position of the knee at 90° flexion was accepted as the starting angle; i.e., 0°. The patients moved their leg from 0°(starting angle) to 45°, 15° and 60° extension direction in sequence to prevent a learning effect. With eyes open, the patients held their leg at the starting angle for 10 seconds and then moved it to 45° (target angle), held the leg at that angle for 10 seconds, and then returned to the starting angle. This procedure was repeated three times and the patient was encouraged to focus on maintaining the target angle. After keeping their leg at the starting angle for 10 seconds with eyes closed, the patients were asked to move their leg to the 45° angle. The angle predicted by the patients was recorded and the same process was repeated three times. Estimating the target angle procedure was repeated at 45°, 15°, and 60° and for both the more and less affected legs. After the JPS testing, three angles estimated by the patients were averaged, and the angular error (AE) was calculated for each target angle. Absolute angular error (AAE) was calculated by averaging the AEs, regardless of the numbers being negative or positive. The AAE values of the three target angles were averaged to obtain the mean AAEs (MAEs) (11, 12).

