# **The effects of isokinetic exercises on muscle strength, joint position sense, and kinesiophobia in patients with multiple sclerosis: a randomized controlled trial**

## **ABSTRACT**

**Objective:** To evaluate the effects of isokinetic exercises on muscle strength, knee joint position sense, pain, kinesiophobia, and quality of life in patients with multiple sclerosis.

**Design:** Randomized controlled trial.

**Setting:** Outpatient clinic.

**Participants:** Sixty patients with multiple sclerosis.

**Interventions:** Fifty patients were randomized to an isokinetic exercise (n:25) or home exercise programme (n:25).

**Outcome measures:** The outcome measures were the peak torque/body mass index of quadriceps and hamstring muscles at 60°/s and 180°/s velocities, the hamstring/quadriceps ratios at the same velocities, absolute angular errors of the 15°, 45°, and 60° and the mean absolute angular error of joint position sense of the less and more affected knees, and the scores of Multiple Sclerosis Quality of Life-54, Visual Analogue Scale, and Tampa Scale of Kinesiophobia.

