## Evaluation of quality of life

The Multiple Sclerosis Quality of Life-54 (MSQoL-54) is a multidimensional health-related QoL measure that combines both generic and MS-specific symptoms in a single instrument. The cross cultural adaptation and validation of the MSQoL-54 inventory in a Turkish population was undertaken by Idiman E. et al. in 2006 (15). In the current study, we used the total, physical and emotional composite and pain scores of the Turkish MSQoL-54.

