## Statistical Analysis

The data were analyzed using the Statistical Package for the Social Sciences (SPSS) software version 15.0. The sample characteristics were summarized using descriptive statistics. Descriptive statistics tables were created for numerical variables, and frequency tables were constructed for categorical variables for both groups. The Kolmogorov-Smirnov test was used to test the normality of data. The Mann-Whitney U test was conducted to compare the two groups. The Wilcoxon test was performed for the comparison of before and after treatment values within the groups in terms of muscle strength, knee JPS, kinesiophobia, and QoL variables. The Spearman correlation test was utilized for the evaluation of relationships between muscle strength and knee JPS. The level of statistical significance was set at  $p<0.05$ .

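### Dividing peak torque by BMI leaves height in the strength outcome, and the unadjusted between-group test does not commit to a comparison that would remove it

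*Combined protocol and SAP*

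**What the plan says.** All references are to the combined protocol and SAP.

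- The section on muscle strength and JPS testing records "the quadriceps and hamstring peak torque (PT), the peak torque (PT)/body mass index (BMI") and the hamstring/quadriceps ratio at 60°/s and 180°/s. It adds that "Both the more and less affected legs were tested in order".
- The Abstract lists as the strength outcome "the peak torque/body mass index of quadriceps and hamstring muscles at 60°/s and 180°/s velocities", followed by "the hamstring/quadriceps ratios at the same velocities". Raw peak torque is measured but is not in that list.
- The Procedure section gives 25 patients per arm, measured at baseline and at week 8.
- The Statistical Analysis section says "The Mann-Whitney U test was conducted to compare the two groups". It does not say whether the test is applied to week-8 values or to changes, and it adjusts for neither baseline, height nor sex. It also plans Wilcoxon tests within each group and Spearman correlations of muscle strength with knee JPS, without saying which strength measure the correlations use.

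No reason is given for choosing BMI as the divisor, and torque per kg of body mass is not mentioned.

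**The concern.** A strength index is normally divided by a measure of body size so that large and small patients can be compared. BMI is a poor divisor for this purpose because height has already been divided out of it. The index therefore leaves in whatever relation torque has to height, and through height to sex.

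This matters wherever levels are compared between patients. With 25 per arm, extra between-patient spread costs power in a test of week-8 values. It also makes the outcome harder to interpret, since two patients with the same torque per kg get different scores. The plan's silence on how baseline enters the between-group test decides whether the cost is real or close to nil.

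**Working it through.** The documents give no power calculation, effect size, SD, height or sex distribution, so there is no planned figure to reproduce. Steps 1 and 2 use only the documents and algebra. Steps 3 to 5 rest on assumptions, stated as they arise.

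**1. How many outcomes are affected.** PT/BMI: 2 muscles × 2 velocities × 2 legs = 8. H/Q ratio: 2 velocities × 2 legs = 4. JPS, given as "absolute angular errors of the 15°, 45°, and 60° and the mean absolute angular error of joint position sense of the less and more affected": 3 angles × 2 knees + 2 means = 8. MSQoL-54, where "we used the total, physical and emotional composite and pain scores of the Turkish MSQoL-54": 4. "Visual Analogue Scale, and Tampa Scale of Kinesiophobia": 2. Total 8 + 4 + 8 + 4 + 2 = 26, of which 8 are PT/BMI. Counting MSQoL-54 once gives 23; adding the 8 raw torque values gives 34. Any body-size divisor cancels in the H/Q ratios, so they are untouched.

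**2. The identity.** PT/BMI = PT ÷ (mass/height²) = (PT/mass) × height². At equal torque per kg:
- 1.75 m against 1.55 m: (1.75/1.55)² = 1.27
- 1.80 m against 1.55 m: (1.80/1.55)² = 1.35

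**3. Added spread when levels are compared.** On the log scale, with s² = ln(1 + CV²) for torque per kg, t² = 4 ln(1 + CVh²) for height squared, and correlation ρ between them, the variance ratio of PT/BMI to PT/kg is (s² + t² + 2ρst)/s².
- CV 25%, CVh 4%, ρ = 0: (0.0606 + 0.0064)/0.0606 = 1.105
- CV 50%, CVh 4%, ρ = 0: 1.029
- CV 25%, CVh 5.5%, ρ = 0.3: 1.467

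A simulation with sex made explicit assumed 50% to 100% women, height SD 6.5 to 7 cm within sex, CV 25% to 45%, and men 0% to 20% stronger per kg. It gave ratios of 1.04 to 1.41. A hand check of the two ends, taking mean heights of 1.62 m (women) and 1.75 m (men) and SD 7 cm:
- All women, CV 45%: (0.1844 + 0.0075)/0.1844 = 1.04.
- Half women, CV 25%, men 20% stronger per kg: the sex term is (ln 1.2 ÷ 2)² = 0.0083 for PT/kg and ((ln 1.2 + 2 ln(1.75/1.62)) ÷ 2)² = 0.0283 for PT/BMI. The ratio is (0.0606 + 0.0069 + 0.0283)/(0.0606 + 0.0083) = 1.39, close to the simulated 1.41.

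In patients, 50 × (1 − 1/1.04) ≈ 2 and 50 × (1 − 1/1.41) ≈ 15 of the 50.

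**4. Effect on the planned test.** Simulated Mann-Whitney power at 25 per arm, 3,000 trials per setting. Assumptions: 70% women, the same mean heights, men 25% stronger per kg, within-patient log SD 0.15.

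| Setting | PT/kg | PT/BMI |
|---|---|---|
| Week 8, log effect 0.30, CV 25% | 0.906 | 0.824 |
| Week 8, log effect 0.30, CV 40% | 0.653 | 0.592 |
| Change, log effect 0.12, CV 25% | 0.736 | 0.728 |
| Change, log effect 0.12, CV 40% | 0.709 | 0.707 |
| Week 8, no effect, CV 25% | 0.049 | 0.050 |
| Week 8, no effect, CV 40% | 0.045 | 0.047 |

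The last two rows are type I error, near 0.05 for both measures.

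**5. Divisor against baseline.** For the same log effect of 0.12 at CV 25%, a week-8 comparison has power 0.253 (PT/kg) or 0.215 (PT/BMI), against 0.736 or 0.728 on changes. Under these assumptions, using the baseline value matters far more than the choice of divisor.

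**The case against.** The strongest reply is that this is a preference and not an error. The plan uses BMI consistently, the testing section cites a source for its strength measures that cannot be consulted here, and nothing says that body mass was intended. That stands: a reader might infer that BMI was written by mistake for body mass, and the documents do not support it.

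The claim that PT/kg is less noisy is also conditional. Suppose log torque rises with log height with slope b at fixed BMI. The leftover height variance is proportional to b² for PT/BMI and to (b − 2)² for PT/kg, so PT/kg is quieter only if b > 1. The calculations above take torque per kg as unrelated to height within sex (b = 2) or positively related to it. The documents do not establish the slope in patients with neurological weakness. This is a good reason not to replace PT/BMI by PT/kg outright. It does not rescue BMI as a size correction, because dividing by it leaves the slope at b, whatever b is.

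A reader might also infer that a chance height imbalance biases the comparison. It does not. With an assumed height SD of 9 cm and mean of 166 cm, one standard error of imbalance is 9 × √(2/25) = 2.5 cm, or 2 × 2.5/166 ≈ 3% in PT/BMI. The contrast's own standard error is 7% to 13% (CV 25% to 45% × √(2/25)). The shift is part of the variance already counted, not a second harm.

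Finally, a reader might infer that height contaminates the strength–JPS correlations. The plan does not say that PT/BMI enters them, and no link between height and position error is shown.

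Height is fixed within a patient, so it cannot reverse the sign of any change, and its effect on change scores is negligible. If the sponsor meant changes, little is lost. The plan does not say so.

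**Conclusion.** A minor point that holds in a limited form. The identity is exact, so PT/BMI does not remove body size, and this affects 8 of the 26 listed outcomes. If the Mann-Whitney test is run on week-8 values, height and sex differences can reduce its precision, illustratively by 4% to 41% more variance than torque per kg. That range depends on assumed height, sex mix and torque spread, and on torque rising with height steeply enough. If the test is run on changes, the loss is negligible. No bias and no inflation of type I error are shown under randomisation. The case for changing the analysis does not depend on which divisor is better: adjusting raw torque for its own baseline takes up stable body-size differences with no divisor at all.

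**What to change.** - **Statistical Analysis:** make the between-group strength analysis a comparison of week-8 raw peak torque, adjusted for the baseline value of the same measure, for example by ANCOVA or a rank-based equivalent. Align the Abstract's outcome list with it.
- **Reporting:** keep PT/BMI as a secondary outcome, with the reason for using it, and report torque per kg alongside, provided that body mass was kept from the BMI calculation.
- **Correlations:** state which strength measure enters the Spearman tests, preferably not PT/BMI alone.

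The cost is a little extra analysis of data already collected, and a main strength measure that differs from reports using PT/BMI. Keeping PT/BMI preserves comparability and avoids dropping a listed outcome. The Methods section dates recruitment from June 2016 to June 2017, so if results had been seen before the change, the raw-torque analysis should be labelled as added afterwards.

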#### Evaluation of pain and kinesiophobia

Pain intensity was evaluated with the Visual Analogue Scale (VAS). Using a ruler, a 10 cm line was drawn which provided a range of scores from 0-100. Then the patients marked the point that showed their pain intensity on this line. A higher score in VAS indicates greater pain intensity (13). Kinesiophobia was evaluated using the Tampa Scale of Kinesiophobia (TSK), which is a 17-item self-report survey based on a four-point Likert scale developed as a measurement tool for fear of movement and/or (re)injury. If the total score was above 37 points, the patient was considered to have a high level of kinesiophobia (14).

## Evaluation of quality of life

The Multiple Sclerosis Quality of Life-54 (MSQoL-54) is a multidimensional health-related QoL measure that combines both generic and MS-specific symptoms in a single instrument. The cross cultural adaptation and validation of the MSQoL-54 inventory in a Turkish population was undertaken by Idiman E. et al. in 2006 (15). In the current study, we used the total, physical and emotional composite and pain scores of the Turkish MSQoL-54.

## Interventions

### Isokinetic training program

Before the exercise program, the patients performed hamstring and quadriceps stretching exercises and on-site counting for five minutes. After the warm-up, the patients did concentric/concentric quadriceps and hamstring muscle strengthening exercises in increasing intensity, to the extent that they could tolerate. The isokinetic exercise program was implemented over eight weeks, twice a week on non-consecutive days under the supervision of a doctor. The number of repetitions undertaken by the patients over the program were as follows: first week 5 at 60°/s and 10 at 180°/s, second week 10 at 60°/s and 15 at 180°/s, third week 15 at 60°/s and 20 at 180°/s, fourth week 20 at 60°/s and 30 at 180°/s, and in the last four weeks 20 at 60°/s and 40 at 180°/s angular velocities. Each block of 10 repetitions were performed as a set.

### Home exercise program

The patients undertook lower extremity strengthening and balance exercises three times a week for eight weeks without supervision. They started with three repetitions, which was gradually increased to 10-15. The patients were called two times a week to inquire about exercise continuity and encouraged to undertake the recommended exercises.

## Statistical Analysis

The data were analyzed using the Statistical Package for the Social Sciences (SPSS) software version 15.0. The sample characteristics were summarized using descriptive statistics. Descriptive statistics tables were created for numerical variables, and frequency tables were constructed for categorical variables for both groups. The Kolmogorov-Smirnov test was used to test the normality of data. The Mann-Whitney U test was conducted to compare the two groups. The Wilcoxon test was performed for the comparison of before and after treatment values within the groups in terms of muscle strength, knee JPS, kinesiophobia, and QoL variables. The Spearman correlation test was utilized for the evaluation of relationships between muscle strength and knee JPS. The level of statistical significance was set at  $p<0.05$ .

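### The randomised comparison has no between-group estimate, baseline adjustment or confidence interval, and the plan does not say that it, rather than the within-group tests, decides the treatment effect

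*Combined protocol and SAP*

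**What the plan says.** The Statistical Analysis section is the whole analysis plan. The comparison between arms gets one sentence: "The Mann-Whitney U test was conducted to compare the two groups". The values compared are not named. The Wilcoxon test, by contrast, is described as being "for the comparison of before and after treatment values within the groups in terms of muscle strength, knee JPS, kinesiophobia, and QoL variables".

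The rest of the section covers descriptive tables, a normality test, Spearman correlations and a 0.05 significance level. Neither this section nor any other gives a between-group difference, a confidence interval, a baseline adjustment or a statement of which test carries the treatment conclusion.

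Three other places bear on the point:

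- **Procedure:** "The outcome measures were assed initially and at eighth week after the treatment". A baseline value therefore exists for each outcome. The follow-up is called week 8 below.
- **Introduction:** the aims include "the effects of isokinetic exercises on these variables".
- **Home exercise program:** the comparator is active. "The patients undertook lower extremity strengthening and balance exercises three times a week for eight weeks without supervision".

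**The concern.** What isokinetic training adds to home exercise can be answered only by contrasting the randomised arms. Patients in both arms do strengthening work, so both may improve. A before-to-after change in the isokinetic arm then mixes the added effect with whatever exercise, time and retesting produce in either arm.

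The plan names its outcomes only for the within-arm tests and does not rank the two kinds of test. It thus leaves room to conclude that isokinetic exercise works because its arm reached significance and the other did not. It also leaves room for the Mann-Whitney test to have been a baseline check only. Neither is a stated rule; both are readings that the wording allows.

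Even on the favourable reading, the result is a bare p-value. With 25 per arm, a non-significant p-value does not show whether a useful difference has been excluded.

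**Working it through.** **Inputs from the documents.** There are 25 patients per arm, with assessments at baseline and week 8 (Procedure). The significance level is 0.05, with sidedness not stated and two-sided assumed here; tests are Mann-Whitney between arms and Wilcoxon within arms (Statistical Analysis). The plan gives no power, SD or effect size, so there is no figure of its own to reproduce.

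**Assumed.** Effect sizes, the baseline to week-8 correlation r (0.3 to 0.9) and the distributions (normal or lognormal). Step 1 uses the SD of change as its unit. Steps 2 and 3 use the SD of the outcome; for the lognormal case the shift is on the log scale. With equal SDs at both times, the SD of change is √(2(1−r)) outcome SDs.

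**Step 1. Reading the effect from within-arm tests.** Suppose both arms truly improve by the same amount d. The chance that one arm is significant is approximately p = Φ(5d − 1.96) + Φ(−5d − 1.96), because √25 = 5. The chance that only the isokinetic arm is significant is p(1−p). At d = 0.4, p = 0.516 and p(1−p) = 0.25. Simulation with Wilcoxon tests (40,000 trials per setting), counting a significant improvement in the isokinetic arm and no significance in the home arm, gives:

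| Change in both arms (SD of change) | 0 | 0.2 | 0.3 | 0.4 | 0.5 | 0.6 | 0.8 | 1.0 |
|---|---|---|---|---|---|---|---|---|
| Only isokinetic arm significant (%) | 2 | 13 | 21 | 25 | 23 | 16 | 4 | 0.4 |

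For changes of 0.2 to 0.6, Mann-Whitney on change is non-significant in 85 to 90% of those trials. The opposite failure also occurs: if home exercise improves by 0.8 SD and isokinetic by 1.3 SD, both arms are significant in 96% of trials, and the within-arm tests do not show the difference.

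**Step 2. Power for a 0.5 SD difference between arms** (20,000 trials per cell; %):

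| r | 0.3 | 0.5 | 0.7 | 0.8 | 0.9 |
|---|---|---|---|---|---|
| Normal: Mann-Whitney, week 8 | 39–40 | 39–40 | 39–40 | 39–40 | 39–40 |
| Normal: Mann-Whitney, change | 29 | 39 | 59 | 76 | 96 |
| Normal: ANCOVA | 43 | 51 | 67 | 81 | 98 |
| Normal: rank ANCOVA | 41 | 48 | 62 | 76 | 94 |
| Lognormal: Mann-Whitney, week 8 | 39–40 | 39–40 | 39–40 | 39–40 | 39–40 |
| Lognormal: Mann-Whitney, change | 31 | 40 | 58 | 75 | 95 |
| Lognormal: untransformed ANCOVA | 37 | 44 | 56 | 70 | 92 |
| Lognormal: rank ANCOVA | 42 | 48 | 62 | 76 | 94 |
| Lognormal: ANCOVA on logs | 44 | 51 | 67 | 82 | 97 |

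The lognormal data have a log-SD of 0.6. Type I error was 4.6 to 5.3% in every cell. A Mann-Whitney test on baseline values rejects in 5% of trials throughout, so it says nothing about treatment.

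As a hand check on normal data at r = 0.7, power ≈ Φ(0.5 / (k√(2/25)) − 1.96). Here k is 1 for week-8 values, √(2(1−r)) = 0.775 for change and √(1−r²) = 0.714 for ANCOVA. This gives 42, 63 and 70%. It ignores the t quantile and the small cost of ranks, so it sits slightly above the simulated 39, 59 and 67%.

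**Step 3. Half-width of the 95% CI for a mean difference, normal data.** Week-8 values: t(0.975, 48) × √(2/25) = 0.57 SD. Change: 0.57 × √(2(1−r)). ANCOVA: simulated mean.

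| r | 0.3 | 0.5 | 0.7 | 0.8 | 0.9 |
|---|---|---|---|---|---|
| Week 8 | 0.57 | 0.57 | 0.57 | 0.57 | 0.57 |
| Change | 0.67 | 0.57 | 0.44 | 0.36 | 0.25 |
| ANCOVA | 0.55 | 0.50 | 0.41 | 0.34 | 0.25 |

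The ANCOVA interval is on average no wider than either alternative at any of these correlations.

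**The case against.** The plan does contain a between-group test, it is valid under randomisation, and the natural reading in a two-arm trial is that it compares the treatments. Step 1 therefore measures the consequence of a rule that the plan does not state. Reporting the Mann-Whitney test on change would usually expose the error, and the risk is small once both arms improve by 0.8 SD or more. This stands: Step 1 is the risk left open by the wording, not an expected error rate.

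The efficiency gain is also conditional. Against change scores on normal data, ANCOVA adds 14 points at r = 0.3 but only about 1 at 0.9, and rank ANCOVA goes from +12 to −2. On skewed data, untransformed ANCOVA gains nothing over week-8 values at r = 0.3 and is 2 to 5 points below change at 0.7 or above. The large gains (28 to 58 points) need both week-8 input and a correlation of at least 0.7, and the documents establish neither. This stands too, so lack of adjustment alone would be a minor point.

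On the remedy, rank ANCOVA gives no estimate in outcome units. A percentile bootstrap of the ANCOVA effect covered 93 to 94% in a check on lognormal data, against 95 to 96% for the ordinary t interval. A Hodges-Lehmann difference in change with its interval would sit closer to the planned test. Finally, the Introduction has descriptive and correlational aims besides the treatment effect.

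None of this supplies the missing estimate and interval or says which comparison decides.

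**Conclusion.** The concern holds and should be fixed. It rests on the text alone: the planned between-group analysis is an unadjusted test on unspecified values, with no estimate, no interval and no stated role in the conclusion. The test is not invalid.

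The missing estimate and interval are the main loss. Even an unadjusted week-8 interval would extend about 0.57 SD either side, so a p-value alone leaves a null result hard to interpret. The power loss is real under many but not all of the assumed conditions. Against week-8 values it is small at a correlation of 0.3 and grows with correlation; against change scores it is largest at 0.3 and close to nil at 0.9. All these sizes depend on assumed effects, correlations and distributions.

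**What to change.** - Report for each outcome the week-8 difference between arms, adjusted for that outcome's baseline value by ANCOVA, with a 95% CI.
- For clearly skewed outcomes, use rank ANCOVA for the test and a bootstrap interval for the estimate, allowing for slight under-coverage at this sample size. A Hodges-Lehmann difference in change with its CI is an acceptable simpler choice.
- State that conclusions on efficacy rest on this between-group contrast, and label the within-group Wilcoxon results descriptive.
- State which values the Mann-Whitney test compared.

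The cost is wording and a short analysis. No new patients or measurements are needed, since baseline values are already collected. The section is written in the past tense ("The data were analyzed using the Statistical Package for the Social Sciences (SPSS) software version 15.0"), which suggests that the analysis has been done; in that case the adjusted analysis must be labelled post hoc. This change does not settle multiplicity across the many outcomes listed in the Abstract, which needs its own rule.

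### No primary outcome and no multiplicity control: 26 unranked outcomes, each tested at p<0.05, give 1.3 expected false positives if no outcome truly differs between the arms

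*Combined protocol and SAP*

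**What the plan says.** The Abstract lists the outcomes in one sentence, beginning "The outcome measures were the peak torque/body mass index of quadriceps and hamstring muscles at 60°/s and 180°/s velocities". It goes on to the hamstring/quadriceps ratios, the absolute angular errors at three target angles, "the mean absolute angular error of joint position sense of the less and more affected knees", and then MSQoL-54, VAS and the Tampa scale. None is called primary or secondary.

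The Introduction states the aim for several variables at once: "we aimed to observe the knee JPS and kinesiophobia level, their relationships with QoL, and the effects of isokinetic exercises on these variables".

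Three places in Methods expand the list:
- Muscle strength and JPS testing, on strength: "Both the more and less affected legs were tested in order".
- The same section, on position sense: "The AAE values of the three target angles were averaged to obtain the mean AAEs".
- Evaluation of quality of life: "we used the total, physical and emotional composite and pain scores of the Turkish MSQoL-54".

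The Statistical Analysis section compares the groups by Mann-Whitney without listing the variables. It adds within-group Wilcoxon tests and Spearman correlations, and then gives one threshold for everything: "The level of statistical significance was set at" p<0.05. It contains no hierarchy and no adjustment. The documents give no sample-size calculation from which a primary outcome could be inferred.

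**The concern.** With no ranked outcome, a between-group p<0.05 on any one variable can be reported as evidence that isokinetic exercise works. The plan gives no rule for deciding which significant results count, so the claim can be chosen after the results are known. Effect sizes, and consistency across related outcomes, would still inform a careful reader. The stated significance rule, however, does not limit the chance of a false efficacy claim to 5%.

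**Working it through.** The plan states no outcome count or family-wise error rate, so there is no figure of its own to reproduce. The inputs are the per-test level of 0.05 (Statistical Analysis), 25 patients per arm (Procedure: "Fifty patients were randomized to two groups"), and the outcome list.

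**Step 1: count the outcomes.**

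| Outcome | Expansion | Number |
|---|---|---|
| Peak torque/BMI | 2 muscles x 2 velocities x 2 legs | 8 |
| Hamstring/quadriceps ratio | 2 velocities x 2 legs | 4 |
| Absolute angular error | 3 angles x 2 knees | 6 |
| Mean absolute angular error | 2 knees | 2 |
| MSQoL-54 | total, physical, emotional, pain | 4 |
| VAS and Tampa scale | 1 + 1 | 2 |
| **Total** | | **26** |

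If strength is counted for one leg only, the 12 strength outcomes become 6 and the total is 20. Counting MSQoL-54 as one score gives 23 (17 with one leg). Adding raw peak torque, which the strength section also evaluates, gives 26 + 8 = 34.

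**Step 2: expected false positives when no outcome truly differs.** This is the sum of the per-test levels and holds under any correlation: 26 x 0.05 = 1.30. For 20 outcomes it is 1.00; for 17 and 34 it is 0.85 and 1.70. Without ties, the exact two-sided Mann-Whitney size at 25 per arm is 0.0494, giving 26 x 0.0494 = 1.28 to 1.29.

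**Step 3: chance of at least one false positive.** The correlations are not given, so I assume a common correlation ρ between the k test statistics, with z = 1.96:

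P = 1 − ∫ [Φ((z − √ρ·g)/√(1−ρ)) − Φ((−z − √ρ·g)/√(1−ρ))]^k φ(g) dg

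| Assumed structure, k = 26 | Integration or normal draws | Simulated Mann-Whitney, 25 per arm |
|---|---|---|
| ρ = 0.9 | 17% | 18% |
| ρ = 0.8 | 24% | 26% |
| ρ = 0.7 | 32% | 34% |
| ρ = 0.5 | 48% | 50% |
| ρ = 0.3 | 62% | 62% |
| Built-in links only | 68% | 68% |

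In the last row the mean angular error is the average of its three components, the hamstring/quadriceps ratio is a difference of logs, and everything else is independent (400,000 draws). The simulations used 20,000 to 25,000 trials per setting. For 20 outcomes the range is about 16% to 59%.

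**Step 4: false positives in favour of isokinetic exercise only.** Two-sided rejections split evenly by direction, so the expected count is 1.3/2 = 0.65. Dropping the second Φ term from the formula gives about 8%, 16%, 24% and 32% at ρ = 0.9, 0.7, 0.5 and 0.3, against a nominal 2.5%.

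**Step 5: effect of adjustment.** The first Holm step over 26 tests is 0.05/26 = 0.0019. In the Mann-Whitney simulations this brings the chance of any false positive down to between 1% and 3.5%.

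**Step 6: cost in power.** This is the difference detectable with 80% power at 25 per arm, for normal data: noncentral t with 48 degrees of freedom and noncentrality d·√(25/2). The Mann-Whitney figure divides d by √0.955.

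| Two-sided level | t-test | Mann-Whitney |
|---|---|---|
| 0.05 | 0.81 SD | 0.83 SD |
| 0.05/3 = 0.0167 | 0.94 SD | 0.97 SD |
| 0.05/26 = 0.0019 | 1.17 SD | 1.20 SD (about 1.23 by simulation) |

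**The case against.** **The number 26 is an inference.** It is printed nowhere, and the Abstract attaches the less and more affected knees most directly to position sense. Counts from 17 to 34 can be defended. This stands as a caution about the exact figure. However, the strength section tests both legs and the quality-of-life section names four scores, so 26 is the natural reading. Even 17 outcomes at a correlation of 0.9 give about 15%.

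**The scope of the between-group test is assumed.** The plan does not list the Mann-Whitney variables. That is true, but a restriction would protect only if it were written down.

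**Half of the false positives would favour home exercise, and the plan defines no direction of benefit for the hamstring/quadriceps ratios.** This is correct, and Step 4 separates direction. The one-direction rate is still more than three times nominal at a correlation of 0.9.

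**The 68% figure is implausible.** It treats strength in the two legs and at the two velocities as independent. I agree that it is an upper illustration and should not drive the severity of the point.

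**Holm over overlapping outcomes is conservative, and an exploratory label suits a 50-patient study better.** Holm here does fall below the 5% target and costs considerable power. The exploratory label is a legitimate answer. The plan does not use it: the title and Abstract present a randomised controlled trial of effects.

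**Conclusion.** The concern holds. Under the plan as written, 1.3 false-positive between-group results are expected if isokinetic and home exercise do not differ on any outcome. This rests on 26 outcomes and one test per outcome, and needs no assumption about correlation. The chance of at least one is well above 5% at every correlation examined, from about 17% upward; the exact value is illustrative because the documents give no correlations. The Wilcoxon and Spearman tests come on top and are not in the count. None of this shows that any particular result is false. It is a point that should be corrected, and correcting it is cheap.

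**What to change.** Add an error-control rule to the Statistical Analysis section.

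- **(a)** If a record predating the between-group results supports the choice, or if those results have not been seen: the sponsor names one already defined outcome for each title domain (strength, joint position sense, kinesiophobia) and tests the three between-group comparisons with Holm at an overall two-sided 0.05.
- **(b)** Otherwise: apply Holm across all 26 between-group tests, or label every outcome exploratory. If Holm is used, list the 26 variables so that the family is fixed.

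In either case, report the remaining outcomes, the within-group tests and the correlations as exploratory, with estimates and 95% confidence intervals and no efficacy claim based on significance.

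This changes analysis and reporting wording only and needs no new data. The text is in the past tense, so (a) is open only under its stated condition. The detectable difference (t-test) rises from 0.81 SD to 0.94 SD at the first step of (a), and to 1.17 SD at the first step of Holm over 26, an increase of about 45% (1.17/0.81). The exploratory label costs no power but gives up any confirmatory claim.
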